8.3.2 Vital Signs

The patient’s vital signs will be recorded (heart rate, blood pressure, temperature and respiration rate) at Visit 1 and Visit 3.

Descriptive summaries (number of observations, mean, standard deviation, minimum, median and maximum) will be provided by treatment and visit.

All data will be listed by treatment and patient.

8.4 Multiple Comparisons

No multiple comparison adjustment will be made in this study.

8.5 Methods for Handling Missing Data

For demographic and baseline characteristics, each variable will be analyzed using all available data. Patients with missing data will be excluded only from analyses for which data are not available.

8.6 Interim Analyses

There is no interim analysis planned in this study.

9. TABLE, LISTING AND FIGURE SHELLS

The following shells are provided in order to provide a framework for the display of data from this study. These shells may not be reflective of every aspect of this study but are intended to show the general layout of the Tables, Listings and Figures that will be included in the final clinical study report. Tables, Listings and Figures are numbered following the ICH structure. Table headers, variables names and footnotes will be modified as needed following data analyses. All descriptive and inferential statistical analyses will be performed using SAS[®] statistical software Version 9.4 or higher, unless otherwise noted.

TABLE, LISTING AND FIGURE SHELLS

Programming note:

Put Program Name in the footnote where it is stored, Location of Output stored, and Date and time when the output is generated.

T14.1.1 Summary of Patient's Disposition

Patients Randomized	Test N = xxx n (%)	Reference N = xxx n (%)	Total N = xxx n (%)
Completed Study	xxx (xx.x)	xxx (xx.x)	xxx (xx.x)
Terminated Early	xxx (xx.x)	xxx (xx.x)	xxx (xx.x)
Adverse Event	xxx (xx.x)	xxx (xx.x)	xxx (xx.x)
Lack of efficacy	xxx (xx.x)	xxx (xx.x)	xxx (xx.x)
Protocol Deviation	xxx (xx.x)	xxx (xx.x)	xxx (xx.x)
Pregnancy	xxx (xx.x)	xxx (xx.x)	xxx (xx.x)
etc.			
Other	xxx (xx.x)	xxx (xx.x)	xxx (xx.x)

Test: Permethrin Cream, 5%, (Encube Ethicals)

Reference: Elimate™ Cream (permethrin) 5% (Prestium Pharma, Inc.)

N= number of patients randomized in that particular group; n= number of patient with data available for that particular group;

total % is based on N

PROGRAM: L:\DEV\755\71675502\SAS\PGM\XXXX
 Created on: ddmmmyy hh:mm

OUTPUT: L:\DEV\755\71675502\SAS\OUT\XXXX
 Page 1 of N

T14.1.2 Summary of Protocol Deviations

	Test N = xxx n (%)	Reference N = xxx n (%)	Total N = xxx n (%)
Total Patients with Protocol Deviations	xxx (xx.x)	xxx (xx.x)	xxx (xx.x)
Total Deviations	xxx	xxx	xxx
Lost to Follow-up	xxx	xxx	xxx
Missed Visit	xxx	xxx	xxx
Non-compliance with dosing requirements	xxx	xxx	xxx
Outside Visit Window	xxx	xxx	xxx
Restricted Medication Use	xxx	xxx	xxx
Randomized in Error	xxx	xxx	xxx
Other	xxx	xxx	xxx

Test: Permethrin Cream, 5%, (Encube Ethicals)

Reference: Elimite™ Cream (permethrin) 5% (Prestium Pharma, Inc.)

N= number of patients randomized in that particular group; n= number of patient with data available for that particular group;
total % is based on N

PROGRAM: L:\DEV\755\71675502\SAS\PGM\XXXX
Created on: ddmmmyy hh:mm

OUTPUT: L:\DEV\755\71675502\SAS\OUT\XXXX
Page 1 of N

**T14.1.3.1 Summary of Patients Excluded from Efficacy Analysis
(Population Determination)**

	Test N = xxx n (%)	Reference N = xxx n (%)	Total N = xxx n (%)
Safety Population	xxx (xx.x)	xxx (xx.x)	xxx (xx.x)
Excluded from Safety population	xxx (xx.x)	xxx (xx.x)	xxx (xx.x)
PP Population	xxx (xx.x)	xxx (xx.x)	xxx (xx.x)
Excluded from PP population	xxx (xx.x)	xxx (xx.x)	xxx (xx.x)
Inclusion/Exclusion criteria not met	xxx (xx.x)	xxx (xx.x)	xxx (xx.x)
Non-compliant with dosing requirement	xxx (xx.x)	xxx (xx.x)	xxx (xx.x)
Major protocol deviations	xxx (xx.x)	xxx (xx.x)	xxx (xx.x)
etc.	xxx (xx.x)	xxx (xx.x)	xxx (xx.x)
	xxx (xx.x)	xxx (xx.x)	xxx (xx.x)

Test: Permethrin Cream, 5%, (Encube Ethicals)

Reference: Elimite™ Cream (permethrin) 5% (Prestium Pharma, Inc.)

N= number of patients randomized in that particular group; n= number of patient with data available for that particular group;
total % is based on N

PROGRAM: L:\DEV\755\71675502\SAS\PGM\XXXX
Created on: ddmmmyy hh:mm

OUTPUT: L:\DEV\755\71675502\SAS\OUT\XXXX
Page 1 of N

T14.1.3.2 Summary of Patients Included in Analysis Population by Study Center

Site No.	Name	Total Randomized	PP			Safety		
			Test	Reference	Total	Test	Reference	Total
XX	XXXX	XXX	XXX	XXX	XXX	XXX	XXX	XXX
XX	XXXX	XXX	XXX	XXX	XXX	XXX	XXX	XXX

Test: Permethrin Cream, 5%, (Encube Ethicals)
 Reference: Elimite™ Cream (permethrin) 5% (Prestium Pharma, Inc.)

PROGRAM: L:\DEV\755\71675502\SAS\PGM\XXXX
 Created on: ddmmmyy hh:mm

OUTPUT: L:\DEV\755\71675502\SAS\OUT\XXXX
 Page 1 of N

T14.1.3.3 Study Timelines (Screened subjects)

	Trial Timelines
	Date
First Patient First Visit (FPFV)	mm-DDD-YYYY
Last Patient Last Visit (LPLV)	mm-DDD-YYYY
Trial Duration (Days)	xxx

Note: Trial Duration (Days) = (Date of LPLV - Date of FPFV) + 1

PROGRAM: L:\DEV\755\71675502\SAS\PGM\XXXX
Created on: ddmmmyy hh:mm

OUTPUT: L:\DEV\755\71675502\SAS\OUT\XXXX
Page 1 of N

**T14.1.4 Summary of Demographic Data and Baseline Characteristics
(Safety Population)**

		Test n = xxx n (%)	Reference n = xxx n (%)	Total N = xxx n (%)	P-value
Age (years)	n	xxx	xxx	xxx	x.xxxx
	Mean ± SD	xx.x ± xx.x	xx.x ± xx.x	xx.x ± xx.x	
	Median	xx.x	xx.x	xx.x	
	Range	xx.x - xx.x	xx.x - xx.x	xx.x - xx.x	
Age Groups	< 18	xxx (xx.x)	xxx (xx.x)	xxx (xx.x)	x.xxxx
	18 – 40	xxx (xx.x)	xxx (xx.x)	xxx (xx.x)	
	41 – 64	xxx (xx.x)	xxx (xx.x)	xxx (xx.x)	
	65 – 75	xxx (xx.x)	xxx (xx.x)	xxx (xx.x)	
	> 75	xxx (xx.x)	xxx (xx.x)	xxx (xx.x)	
Race	American Indian or Alaska Native	xxx (xx.x)	xxx (xx.x)	xxx (xx.x)	x.xxxx
	Asian	xxx (xx.x)	xxx (xx.x)	xxx (xx.x)	
	Black/African American	xxx (xx.x)	xxx (xx.x)	xxx (xx.x)	
	Native Hawaiian or other Pacific Islander	xxx (xx.x)	xxx (xx.x)	xxx (xx.x)	
	White	xxx (xx.x)	xxx (xx.x)	xxx (xx.x)	
	Other	xxx (xx.x)	xxx (xx.x)	xxx (xx.x)	
Ethnicity	Hispanic or Latino	xxx (xx.x)	xxx (xx.x)	xxx (xx.x)	x.xxxx
	Not Hispanic or Latino	xxx (xx.x)	xxx (xx.x)	xxx (xx.x)	

Test: Permethrin Cream, 5%, (Encube Ethicals)

Reference: Elimite™ Cream (permethrin) 5% (Prestium Pharma, Inc.)

N= number of patients randomized in that particular group; n= number of patient with data available for that particular group; total % is based on N

**T14.1.4 Summary of Demographic Data
(Safety Population)**

		Test N = xxx n (%)	Reference N = xxx n (%)	Total N = xxx n (%)	P-value
Sex	Female	xxx (xx.x)	xxx (xx.x)	xxx (xx.x)	x.xxxx
	Male	xxx (xx.x)	xxx (xx.x)	xxx (xx.x)	
Baseline Severity Score of Nocturnal Itching Pretreatment	None	xxx (xx.x)	xxx (xx.x)	xxx (xx.x)	x.xxxx
	Mild	xxx (xx.x)	xxx (xx.x)	xxx (xx.x)	
	Moderate	xxx (xx.x)	xxx (xx.x)	xxx (xx.x)	
	Severe	xxx (xx.x)	xxx (xx.x)	xxx (xx.x)	
Baseline Severity of Lesion Count Infestation Pretreatment	Mild	xxx (xx.x)	xxx (xx.x)	xxx (xx.x)	x.xxxx
	Moderate	xxx (xx.x)	xxx (xx.x)	xxx (xx.x)	
	Severe	xxx (xx.x)	xxx (xx.x)	xxx (xx.x)	

Test: Permethrin Cream, 5%, (Encube Ethicals)

Reference: Elimite™ Cream (permethrin) 5% (Prestium Pharma, Inc.)

N= number of patients randomized in that particular group; n= number of patient with data available for that particular group; total % is based on N

PROGRAM: L:\DEV\755\71675502\SAS\PGM\XXXX
Created on: dmmmyy hh:mm

OUTPUT: L:\DEV\755\71675502\SAS\OUT\XXXX
Page 1 of N

Similar tables will be created for T14.1.5.

T14.1.5 Summary of Demographic Data (Per-Protocol Population)

**T14.1.6 Summary of Microscopic Evaluation of Scabies
(Per-Protocol Population)**

Visit	Microscopic Evaluation	Statistic	Test N = xxx n (%)	Reference N = xxx n (%)
1 (Baseline)	Microscopic examination result	Positive	xxx (xx.x)	xxx (xx.x)
		Negative	xxx (xx.x)	xxx (xx.x)
	Number of scraped sites	n	xxx	xxx
		Mean ± SD	xx.x ± xx.x	xx.x ± xx.x
		Median	xx.x	xx.x
		Range	xx.x - xx.x	xx.x - xx.x
2	Microscopic examination result	Positive	xxx (xx.x)	xxx (xx.x)
		Negative	xxx (xx.x)	xxx (xx.x)
	Number of scraped sites	n	xxx	xxx
		Mean ± SD	xx.x ± xx.x	xx.x ± xx.x
		Median	xx.x	xx.x
		Range	xx.x - xx.x	xx.x - xx.x
3 (EOS)	Microscopic examination result	Positive	xxx (xx.x)	xxx (xx.x)
		Negative	xxx (xx.x)	xxx (xx.x)
	Number of scraped sites	n	xx	xx
		Mean ± SD	xx.x ± xx.x	xx.x ± xx.x
		Median	xx.x	xx.x
		Range	xx.x - xx.x	xx.x - xx.x

Test: Permethrin Cream, 5%, (Encube Ethicals)

Reference: Elimite™ Cream (permethrin) 5% (Prestium Pharma, Inc.)

N= number of patients randomized in that particular group; n= number of patient with data available for that particular group; total % is based on N

**T14.1.7 Summary of Frequency of Scabies Signs and Symptoms Rating
(Per-Protocol Population)**

Visit	Grade (Lesion Count)	Test N = xxx n (%)	Reference N = xxx n (%)
1	Mild (<50)	xxx (xx.x)	xxx (xx.x)
	Moderate (50 – 100)	xxx (xx.x)	xxx (xx.x)
	Severe (>100)	xxx (xx.x)	xxx (xx.x)
2	Mild (<50)	xxx (xx.x)	xxx (xx.x)
	Moderate (50 – 100)	xxx (xx.x)	xxx (xx.x)
	Severe (>100)	xxx (xx.x)	xxx (xx.x)
3	Mild (<50)	xxx (xx.x)	xxx (xx.x)
	Moderate (50 – 100)	xxx (xx.x)	xxx (xx.x)
	Severe (>100)	xxx (xx.x)	xxx (xx.x)

Test: Permethrin Cream, 5%, (Encube Ethicals)

Reference: Elimite™ Cream (permethrin) 5% (Prestium Pharma, Inc.)

N= number of patients randomized in that particular group; n= number of patient with data available for that particular group; total % is based on N

PROGRAM: L:\DEV\755\71675502\SAS\PGM\XXXX
Created on: ddmmmyy hh:mm

OUTPUT: L:\DEV\755\71675502\SAS\OUT\XXXX
Page 1 of N

**T14.1.8.1 Summary of Equivalence Analysis Results of Primary Efficacy Endpoint
(Proportion of Patients in each Treatment Group with Therapeutic Cure (Parasitological Cure plus Clinical Cure)
of Scabies at Day 28 ± 4)
(Per-Protocol Population)**

Treatment Group	Number of Patients (N)	Number of Patients with Therapeutic Cure (n)	Proportion of Therapeutic Cure (%)	Difference Between Treatments	
				Difference (%)	90% CI Evaluation
Test	Xxx	xxx	xx.x		
Reference	Xxx	xxx	xx.x	xx.x	xx.x – xx.x

Test: Permethrin Cream, 5%, (Encube Ethicals)

Reference: Elimite™ Cream (permethrin) 5% (Prestium Pharma, Inc.)

PROGRAM: L:\DEV\755\71675502\SAS\PGM\XXXX
Created on: ddmmmyy hh:mm

OUTPUT: L:\DEV\755\71675502\SAS\OUT\XXXX
Page 1 of N

**T14.1.8.2 Sensitivity Analysis Summary of Equivalence Analysis Results of Primary Efficacy Endpoint
(Proportion of Patients in each Treatment Group with Therapeutic Cure (Parasitological Cure plus Clinical Cure)
of Scabies at Day 28 ± 4)
(Safety Population)**

**T14.1.9.1 Supportive Analysis #1: Summary of Equivalence Analysis Results of Primary Efficacy Endpoint
(Per-Protocol Population)**

Treatment Group	Number of Patients (N)	Number of Patients with Therapeutic Cure (n)	Proportion of Therapeutic Cure (%)	Difference Between Treatments	
				Difference (%)	90% CI Evaluation
Test	Xxx	xxx	xx.x		
Reference	Xxx	xxx	xx.x	xx.x	xx.x – xx.x

Test: Permethrin Cream, 5%, (Encube Ethicals)

Reference: Elimite™ Cream (permethrin) 5% (Prestium Pharma, Inc.)

The primary analysis will be performed including patients who completed Visit 2 within 14 ± 2 days and Visit 3 within 28 ± 4 days.

PROGRAM: L:\DEV\755\71675502\SAS\PGM\XXXX
Created on: ddmmmyy hh:mm

OUTPUT: L:\DEV\755\71675502\SAS\OUT\XXXX
Page 1 of N

**T14.1.9.2 Supportive Analysis #2: Summary of Equivalence Analysis Results of Primary Efficacy Endpoint
(Per-Protocol Population)**

Note: The primary analysis will be performed including patients who completed Visit 2 within 14 ± 2 days and Visit 3 between Day 26 and Day 32, inclusive.

**T14.1.9.3 Supportive Analysis #3: Summary of Equivalence Analysis Results of Primary Efficacy Endpoint
(Per-Protocol Population)**

Note: The primary analysis will be performed including patients who completed Visit 2 within 14 ± 2 days and Visit 3 within 28 ± 2 days.

**T14.1.10 Summary of Frequency of Patient Pruritus Assessment
(Per-Protocol Population)**

Visit	Grade (Score)	Test N = xxx n (%)	Reference N = xxx n (%)
1	NONE: Complete absence of itching (0)	xxx (xx.x)	xxx (xx.x)
	MILD: Slight itching, no sleep loss (1)	xxx (xx.x)	xxx (xx.x)
	MODERATE: Definitely present, interrupts sleep (2)	xxx (xx.x)	xxx (xx.x)
	SEVERE: Marked, intense, cannot sleep (3)	xxx (xx.x)	xxx (xx.x)
2	NONE: Complete absence of itching (0)	xxx (xx.x)	xxx (xx.x)
	MILD: Slight itching, no sleep loss (1)	xxx (xx.x)	xxx (xx.x)
	MODERATE: Definitely present, interrupts sleep (2)	xxx (xx.x)	xxx (xx.x)
	SEVERE: Marked, intense, cannot sleep (3)	xxx (xx.x)	xxx (xx.x)
3	NONE: Complete absence of itching (0)	xxx (xx.x)	xxx (xx.x)
	MILD: Slight itching, no sleep loss (1)	xxx (xx.x)	xxx (xx.x)
	MODERATE: Definitely present, interrupts sleep (2)	xxx (xx.x)	xxx (xx.x)
	SEVERE: Marked, intense, cannot sleep (3)	xxx (xx.x)	xxx (xx.x)

Test: Permethrin Cream, 5%, (Encube Ethicals)

Reference: Elimite™ Cream (permethrin) 5% (Prestium Pharma, Inc.)

N= number of patients randomized in that particular group; n= number of patient with data available for that particular group; total % is based on N

PROGRAM: L:\DEV\755\71675502\SAS\PGM\XXXX
Created on: ddmmmyy hh:mm

OUTPUT: L:\DEV\755\71675502\SAS\OUT\XXXX
Page 1 of N

T14.1.11 Overall Summary of Adverse Events
(Safety Population)

Description	Test	Reference	Total
Subjects in Safety Analysis Set	xxx	xxx	xxx
Subjects with at least one AE	xxx (xx.x)	xxx (xx.x)	xxx (xx.x)
Discontinued study drug due to above AE	xxx (xx.x)	xxx (xx.x)	xxx (xx.x)
AEs reported	xxx	xxx	xxx
Mild	xxx (xx.x)	xxx (xx.x)	xxx (xx.x)
Moderate	xxx (xx.x)	xxx (xx.x)	xxx (xx.x)
Severe	xxx (xx.x)	xxx (xx.x)	xxx (xx.x)
Not Related	xxx (xx.x)	xxx (xx.x)	xxx (xx.x)
Related	xxx (xx.x)	xxx (xx.x)	xxx (xx.x)
Death	xxx (xx.x)	xxx (xx.x)	xxx (xx.x)
Serious AE	xxx (xx.x)	xxx (xx.x)	xxx (xx.x)

Test: Permethrin Cream, 5%, (Encube Ethicals)
Reference: Elimite™ Cream (permethrin) 5% (Prestium Pharma, Inc.)

Note: subjects having multiple AEs within same system organ class were counted only once in respective system organ class.
Under any event subjects having multiple AEs with same Preferred Term were counted only once within the respective preferred term.

T14.1.12 Summary of Frequency of Adverse Events by Body System
(Safety Population)

Body System	Preferred Term	Test N = xxx		Reference N = xxx		Fisher's p-value
		Events	Patients n (%)	Events	Patients n (%)	
Patients with at least one AE	Total	xx	xxx (xx.x)	xx	xxx (xx.x)	x.xxxx
Ear and labyrinth disorders	Ear pain etc.	xx	xxx (xx.x)	xx	xxx (xx.x)	x.xxxx
etc.						

Test: Permethrin Cream, 5%, (Encube Ethicals)

Reference: Elimite™ Cream (permethrin) 5% (Prestium Pharma, Inc.)

N= number of patients in safety population in that particular group; n= number of patient with data available for that particular group;
total % is based on N

PROGRAM: L:\DEV\755\71675502\SAS\PGM\XXXX
Created on: ddmmmyy hh:mm

OUTPUT: L:\DEV\755\71675502\SAS\OUT\XXXX
Page 1 of N

**T14.1.13 Summary of Frequency of Adverse Events by Relationship
(Safety Population)**

Body System	Preferred Term	Test # of Events (N = xxx)		Reference # of Events (N = xxx)	
		Related n (%)	Not Related n (%)	Related n (%)	Not Related n (%)
Total AEs	Total	xxx (xx.x)	xxx (xx.x)	xxx (xx.x)	xxx (xx.x)
Ear and labyrinth disorders	Ear pain	xxx (xx.x)	xxx (xx.x)	xxx (xx.x)	xxx (xx.x)
	Hypoacusis	xxx (xx.x)	xxx (xx.x)	xxx (xx.x)	xxx (xx.x)

Test: Permethrin Cream, 5%, (Encube Ethicals)

Reference: Elimate™ Cream (permethrin) 5% (Prestium Pharma, Inc.)

N = Total number of events in that particular group group; Percentage is based on total number of events.

PROGRAM: L:\DEV\755\71675502\SAS\PGM\XXXX
Created on: ddmmmyy hh:mm

OUTPUT: L:\DEV\755\71675502\SAS\OUT\XXXX
Page 1 of N

**T14.1.14 Summary of Frequency of Adverse Events by Severity
(Safety Population)**

Body System	Preferred Term	Test # of Events (N = xxx)			Reference # of Events (N = xxx)		
		Mild n (%)	Moderate n (%)	Severe n (%)	Mild n (%)	Moderate n (%)	Severe n (%)
Total AEs	Total	xxx (xx.x)	xxx (xx.x)	xxx (xx.x)	xxx (xx.x)	xxx (xx.x)	xxx (xx.x)
Ear and labyrinth disorders	Ear pain	xxx (xx.x)	xxx (xx.x)	xxx (xx.x)	xxx (xx.x)	xxx (xx.x)	xxx (xx.x)
	Hypoacusis	xxx (xx.x)	xxx (xx.x)	xxx (xx.x)	xxx (xx.x)	xxx (xx.x)	xxx (xx.x)

Test: Permethrin Cream, 5%, (Encube Ethicals)
Reference: Elimate™ Cream (permethrin) 5% (Prestium Pharma, Inc.)
N = Total number of events in that particular group group; Percentage is based on total number of events.

PROGRAM: L:\DEV\755\71675502\SAS\PGM\XXXX
Created on: ddmmmyy hh:mm

OUTPUT: L:\DEV\755\71675502\SAS\OUT\XXXX
Page 1 of N

**T14.1.15 Summary of Frequency of Serious Adverse Events
(Safety Population)**

Body System	Preferred Term	Test # Events	Reference # Events
Injury, poisoning and procedural complications	Alcohol poisoning	xxx	xxx

Test: Permethrin Cream, 5%, (Encube Ethicals)
Reference: Elimite™ Cream (permethrin) 5% (Prestium Pharma, Inc.)

PROGRAM: L:\DEV\755\71675502\SAS\PGM\XXXX
Created on: ddmmmyy hh:mm

OUTPUT: L:\DEV\755\71675502\SAS\OUT\XXXX
Page 1 of N

**T14.1.16 Summary of Vital Signs
(Safety Population)**

Vital Signs	Visit	Statistic	Test N = xxx	Reference N = xxx
Systolic Blood Pressure (mmHg)	1	n	xxx	xxx
		Mean ± SD	xxx.x ± xx.x	xxx.x ± xx.x
		Median	xxx.x	xxx.x
		Range	xxx.x – xxx.x	xxx.x – xxx.x
	3			
Diastolic Blood Pressure (mmHg)				
Pulse Rate (beats/min)				
Respiration Rate (breaths/min)				
Temperature (F)				

Test: Permethrin Cream, 5%, (Encube Ethicals)
Reference: Elimite™ Cream (permethrin) 5% (Prestium Pharma, Inc.)

PROGRAM: L:\DEV\755\71675502\SAS\PGM\XXXX
Created on: ddmmmyy hh:mm

OUTPUT: L:\DEV\755\71675502\SAS\OUT\XXXX
Page 1 of N

**T14.1.17 Summary of Frequency of Patients with Re-Infestation from Day 14 (treatment success) to Day 28 (treatment failure)
(Per-Protocol Population)**

Test (N = xxx) n (%)	Reference (N = xxx) n (%)
xxx (xx.x)	xxx (xx.x)

Test: Permethrin Cream, 5%, (Encube Ethicals)

Reference: Elimite™ Cream (permethrin) 5% (Prestium Pharma, Inc.)

N= number of patients randomized in that particular analysis group; n= number of patient with data available for that particular group;
total % is based on N

PROGRAM: L:\DEV\755\71675502\SAS\PGM\XXXX
Created on: ddmmmyy hh:mm

OUTPUT: L:\DEV\755\71675502\SAS\OUT\XXXX
Page 1 of N

**T14.1.18 Summary of Frequency of Patients who are Therapeutic Failures on Day 14 ± 4
(Per-Protocol Population)**

Test (N = xxx) n (%)	Reference (N = xxx) n (%)
xxx (xx.x)	xxx (xx.x)

Test: Permethrin Cream, 5%, (Encube Ethicals)

Reference: Elimite™ Cream (permethrin) 5% (Prestium Pharma, Inc.)

N= number of patients randomized in that particular analysis group; n= number of patient with data available for that particular group;
total % is based on N

PROGRAM: L:\DEV\755\71675502\SAS\PGM\XXXX
Created on: ddmmmyy hh:mm

OUTPUT: L:\DEV\755\71675502\SAS\OUT\XXXX
Page 1 of N

L16.2.1 Listing of Discontinued Patients

Treatment Group	Patient Randomization Number	Discontinuation Reason	Population
Test	xxxx xxxx	Withdrawal by Patient Lost to Follow-up	Per-Protocol Safety
Reference			

Test: Permethrin Cream, 5%, (Encube Ethicals)
Reference: Elimite™ Cream (permethrin) 5% (Prestium Pharma, Inc.)

PROGRAM: L:\DEV\755\71675502\SAS\PGM\XXXX
Created on: ddmmmyy hh:mm

OUTPUT: L:\DEV\755\71675502\SAS\OUT\XXXX
Page 1 of N

L16.2.2 Listing of Protocol Deviations

Treatment Group	Patient Randomization Number	Event Description	Population
Test	xxxx	Outside Visit Window (Visit 3)	Safety

Reference

Test: Permethrin Cream, 5%, (Encube Ethicals)
Reference: Elimite™ Cream (permethrin) 5% (Prestium Pharma, Inc.)

PROGRAM: L:\DEV\755\71675502\SAS\PGM\XXXX
Created on: ddmmmyy hh:mm

OUTPUT: L:\DEV\755\71675502\SAS\OUT\XXXX
Page 1 of N

L16.2.3 Patients Excluded from the Per-Protocol Population

Treatment Group	Patient Randomization Number	Exclusion Reason
Test	xxxx	Major protocol deviation

Reference

Test: Permethrin Cream, 5%, (Encube Ethicals)
Reference: Elimite™ Cream (permethrin) 5% (Prestium Pharma, Inc.)

PROGRAM: L:\DEV\755\71675502\SAS\PGM\XXXX
Created on: ddmmmyy hh:mm

OUTPUT: L:\DEV\755\71675502\SAS\OUT\XXXX
Page 1 of N

L16.2.4.1 Listing of Demographic Data

Treatment Group	Patient Randomization Number	Age	Sex	Ethnicity	Race
Test	xxxx	30	Female	Not Hispanic or Latino	Black or African American

Reference

Test: Permethrin Cream, 5%, (Encube Ethicals)
Reference: Elimite™ Cream (permethrin) 5% (Prestium Pharma, Inc.)

PROGRAM: L:\DEV\755\71675502\SAS\PGM\XXXX
Created on: ddmmmyy hh:mm

OUTPUT: L:\DEV\755\71675502\SAS\OUT\XXXX
Page 1 of N

L16.2.4.2 Listing of Medical History

Treatment Group	Patient Randomization Number	System	Diagnosis or Surgical Procedure	Start Date	End Date	Ongoing
Test	xxxx	Gynecologic	Menopause	yyyy-mm-dd	yyyy-mm-dd	

Reference

Test: Permethrin Cream, 5%, (Encube Ethicals)
Reference: Elimite™ Cream (permethrin) 5% (Prestium Pharma, Inc.)

PROGRAM: L:\DEV\755\71675502\SAS\PGM\XXXX
Created on: ddmmmyy hh:mm

OUTPUT: L:\DEV\755\71675502\SAS\OUT\XXXX
Page 1 of N

L16.2.4.3 Listing of Concomitant Medication

Treatment Group	Patient Randomization Number	Treatment Area	Medication	Dosage	Frequency	Route	Start/End Date/ Ongoing	Indication
Test	xxxx	No	Lisinopril	20 MG	QD	PO	yyyy-mm-dd / yyyy-mm-dd	Hypertension

Reference

Test: Permethrin Cream, 5%, (Encube Ethicals)
Reference: Elimite™ Cream (permethrin) 5% (Prestium Pharma, Inc.)

PROGRAM: L:\DEV\755\71675502\SAS\PGM\XXXX
Created on: ddmmmyy hh:mm

OUTPUT: L:\DEV\755\71675502\SAS\OUT\XXXX
Page 1 of N

L16.2.4.4 Listing of Treatment for Family Members/Close Contacts

Treatment Group	Patient Randomization Number	Visit Date	How many members in the patient's house-hold (e.g., close personal contacts, and/or family member(s)) are affected with scabies?	Has the patient come into contact with the affected family member(s) and/or close personal contacts?	Have affected family member(s)/close personal contacts of the patient been given prescription generic permethin?
Test	xxxx	yyyy-mm-dd	xxx	Yes	Yes

Reference

Test: Permethrin Cream, 5%, (Encube Ethicals)
 Reference: Elimite™ Cream (permethrin) 5% (Prestium Pharma, Inc.)

PROGRAM: L:\DEV\755\71675502\SAS\PGM\XXXX
 Created on: ddmmmyy hh:mm

OUTPUT: L:\DEV\755\71675502\SAS\OUT\XXXX
 Page 1 of N

L16.2.5.1 Listing of Visit Date Information

Treatment Group	Patient Randomization Number	Informed Consent Signed	Date Assent Signed	Visit 1	Visit 2	Visit 3 / Early Termination	Safety Population	Per-Protocol Population
Test	xxxx	yyyy-mm-dd	yyyy-mm-dd	yyyy-mm-dd	yyyy-mm-dd	yyyy-mm-dd	Yes	No

Reference

Test: Permethrin Cream, 5%, (Encube Ethicals)
Reference: Elimite™ Cream (permethrin) 5% (Prestium Pharma, Inc.)

PROGRAM: L:\DEV\755\71675502\SAS\PGM\XXXX
Created on: ddmmmyy hh:mm

OUTPUT: L:\DEV\755\71675502\SAS\OUT\XXXX
Page 1 of N

L16.2.5.2 Listing of Drug Administration

Treatment Group	Patient Randomization Number	Date of First Dose	Date of Last Dose	Total Doses Applied	Treatment Compliance*
Test	xxxx	yyyy-mm-dd	yyyy-mm-dd	xx	Yes

Reference

Test: Permethrin Cream, 5%, (Encube Ethicals)
Reference: Elimite™ Cream (permethrin) 5% (Prestium Pharma, Inc.)

*Treatment compliance will be calculated based off the following criteria: 1.) all patients randomized will have at least 1 dose, confirmed from the study drug administration form via the eCRF. Date of first and last dose and total confirmed doses applied will confirm treatment use. 2.) A patient who is required to dose a second time, compliance will be calculated using criteria 1 and the following data points (via the eCRF) positive microscopic result at Visit 2 and selection of “yes” regarding the question “based on your assessment and microscopic results, is continued treatment required?”

PROGRAM: L:\DEV\755\71675502\SAS\PGM\XXXX
Created on: ddmmmyy hh:mm

OUTPUT: L:\DEV\755\71675502\SAS\OUT\XXXX
Page 1 of N

L16.2.6.1 Listing of Scabies Signs and Symptoms Rating and Microscopic Evaluation of Scabies

Treatment Group	Patient Randomization Number	Visit	Scabies Lesion Count	Are there any new lesions present?	Have all original lesions healed?	Number of scraped sites	Microscopic Examination Result	Clinical Cure	Parasitological Cure	Therapeutic Cure
Test	xxxx	1	Moderate	NA	NA	3	Positive (mites, eggs)			
		2	Mild	No	No	3	Positive (eggs)			
		3	Mild	No	Yes	NA	0	Negative	Yes	Yes
	xxxx	1	Moderate	NA	NA	3	Positive (eggs)			
		2	Mild	No	No	3	Positive (eggs)			
		3	Mild	Yes	Yes	0	Negative	No	Yes	No

Reference

Test: Permethrin Cream, 5%, (Encube Ethicals)
Reference: Elimite™ Cream (permethrin) 5% (Prestium Pharma, Inc.)

PROGRAM: L:\DEV\755\71675502\SAS\PGM\XXXX
Created on: ddmmmyy hh:mm

OUTPUT: L:\DEV\755\71675502\SAS\OUT\XXXX
Page 1 of N

L16.2.6.2 Listing of Patient Pruritus Assessment

Treatment Group	Patient Randomization Number	Visit 1	Visit 2	Visit 3 / Early Termination	No Itch Persistence
Test	xxxx	1 (Mild) 2 (Moderate)	1 (Mild) 1 (Mild)	0 (None) 1 (Mild)	Yes No

Reference

Test: Permethrin Cream, 5%, (Encube Ethicals)
Reference: Elimite™ Cream (permethrin) 5% (Prestium Pharma, Inc.)

PROGRAM: L:\DEV\755\71675502\SAS\PGM\XXXX
Created on: ddmmmyy hh:mm

OUTPUT: L:\DEV\755\71675502\SAS\OUT\XXXX
Page 1 of N

L16.2.6.3 Listing of Investigator Evaluator Initials On Scabies Signs & Symptoms Rating

Treatment Group	Patient Randomization Number	Visit 1	Visit 2	Visit 3 / Early Termination
Test	xxxx	XYZ	D-G	D-G

Reference

Test: Permethrin Cream, 5%, (Encube Ethicals)
Reference: Elimite™ Cream (permethrin) 5% (Prestium Pharma, Inc.)

PROGRAM: L:\DEV\755\71675502\SAS\PGM\XXXX
Created on: ddmmmyy hh:mm

OUTPUT: L:\DEV\755\71675502\SAS\OUT\XXXX
Page 1 of N

L16.2.7 Listing of Adverse Events by Treatment

Treatment Group	Patient Randomization Number	Body System / MedDRA Term / AE Term	Treatment Area	Start /End Date/ Ongoing	Severity	Relationship to Study Drug	Outcome	Action Taken/ Other Action Taken	SAE	TEAE
Test	xxxx	Nervous system disorders / Headache / Headache	No	yyyy-mm-dd / yyyy-mm-dd	Mild	Related	Recovere d	Dose Not Changed/ None	No	Yes

Reference

Test: Permethrin Cream, 5%, (Encube Ethicals)
Reference: Elimite™ Cream (permethrin) 5% (Prestium Pharma, Inc.)

PROGRAM: L:\DEV\755\71675502\SAS\PGM\XXXX
Created on: ddmmmyy hh:mm

OUTPUT: L:\DEV\755\71675502\SAS\OUT\XXXX
Page 1 of N

L16.2.8.1 Listing of Pregnancy Test Results

Treatment Group	Patient Randomization Number	Visit 1	Visit 3 / Early Termination
Test	xxxx	Negative	Negative

Reference

Test: Permethrin Cream, 5%, (Encube Ethicals)
Reference: Elimite™ Cream (permethrin) 5% (Prestium Pharma, Inc.)

PROGRAM: L:\DEV\755\71675502\SAS\PGM\XXXX
Created on: ddmmmyy hh:mm

OUTPUT: L:\DEV\755\71675502\SAS\OUT\XXXX
Page 1 of N

L16.2.8.2 Listing of Vital Signs

Treatment Group	Patient Randomization Number	Visit	Systolic BP (mmHg)	Diastolic BP (mmHg)	Pulse Rate (beats/min)	Respiration Rate (breaths/min)	Temperature (F)
Test	xxxx	1	120	70	84	18	98.6
		3	140	100 (NCS)	74	18	97.0

[figure not shown]
Reference

Test: Permethrin Cream, 5%, (Encube Ethicals)
Reference: Elimite™ Cream (permethrin) 5% (Prestium Pharma, Inc.)

PROGRAM: L:\DEV\755\71675502\SAS\PGM\XXXX
Created on: ddmmmyy hh:mm

OUTPUT: L:\DEV\755\71675502\SAS\OUT\XXXX
Page 1 of N

F15.1.1 Histogram of Proportion of Patients with Therapeutic Cure on Day 28 \pm 4

Reference:

1. FDA Draft Guidance on Malathion, June 2012.

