### 11.8 Safety Analysis

Adverse events will be classified using standard MedDRA terminology Version 20.0 or higher and summarized by treatment group. Summary tables comparing the type, incidence, date of onset, date of resolution, severity, action taken, outcome and Investigator's opinion of relationship to the study product will be prepared by treatment group. If sufficient data exist, AE frequencies will be compared between treatments using Fisher's exact test or a similar test in the Safety population.

Signs and symptoms of scabies will not be considered AEs, unless in the Investigator's opinion, they have increased in frequency and/or severity to such an extent that the Investigator/patient considers that it is in the patient's best interest to be dropped from continued participation in the study and given alternative therapy for their condition.

Concomitant medication use during the study will be tabulated by patient.

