2. OBJECTIVES

The objectives of this study are to:

1. Evaluate the therapeutic equivalence of the Test formulation, Permethrin Cream, 5% (Encube Ethicals) to the marketed product, Elimite™ Cream (permethrin) 5% (Prestium Pharma, Inc.) in patients with scabies.
2. Compare the safety of Test and Reference treatments in patients with scabies.

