8.3.1 Adverse Events

All the adverse events (AEs) reported throughout the study will be coded and classified according to the MedDRA (Medical Dictionary for Regulatory Activities) coding dictionary (Version 20.0 or higher). Each adverse event is to be evaluated for date of start and end, seriousness, severity, causal relationship with the study drugs, action taken and outcome.

All AEs will be listed by treatment and patient.

A summary table of the number and percent of patients with AEs by system organ class, preferred term, and treatment will be presented. Each patient will be counted only once within each preferred term.

**NOVUM PHARMACEUTICAL RESEARCH SERVICES
STATISTICAL ANALYSIS PLAN**

Permethrin Cream, 5%

Protocol / Study No. 71675502

A frequency summary table of the number of AEs by system organ class, preferred term, severity, and treatment will be presented. Severity will be classified as “Mild”, “Moderate”, or “Severe”.

Similarly, a frequency summary table of the number of AEs by system organ class, preferred term, and relationship to a study drug, and treatment will be presented. Relationship to a study drug will be classified as “Not Related” or “Related”.

Adverse event frequencies will be compared between treatments using Fisher’s exact test.

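### No planned table clearly gives the proportion of Safety-population patients per arm with a related, severe or serious adverse event

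*SAP*

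**What the plan says.** SAP section 2 (and Protocol 9.0) gives the second objective as "Compare the safety of Test and Reference treatments in patients with scabies". Protocol 11.8 promises "Summary tables comparing the type, incidence, date of onset, date of resolution, severity, action taken, outcome" and the investigator's view of relationship, by treatment group.

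SAP 8.3.1 plans three AE summaries:

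- A patient-level table: "A summary table of the number and percent of patients with AEs by system organ class, preferred term, and treatment will be presented".
- An event-level table by severity: "A frequency summary table of the number of AEs by system organ class, preferred term, severity, and treatment will be presented".
- An event-level table by relationship, introduced by "Similarly, a frequency summary table of the number of AEs by system organ class, preferred term, and relationship to a study drug, and treatment".

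The shells in SAP section 9 follow this text. T14.1.12 shows events and patients n (%) with a Fisher p-value, and its footnote reads "N= number of patients in safety population in that particular group". T14.1.13 and T14.1.14 carry a different footnote, which sets N to the arm's event total and adds: "Percentage is based on total number of events". T14.1.15 has one column of event counts per arm and no percentages.

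**The concern.** A percentage whose denominator is the arm's own number of events describes the make-up of that arm's events. It is not the risk to a patient. T14.1.13 and T14.1.14 are both labelled as Safety-population tables, so a reader may take the percentages for incidences.

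In comparing the safety of two creams, the usual questions are how many patients on each had a treatment-related AE, a severe AE or a serious AE. If the planned tables do not answer them, the study report will lack a basic part of the second objective. The event percentages could also mislead when the arms differ in total events or in how events cluster within patients.

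**Working it through.** The plan states no figure to reproduce. The check sets the AE outputs side by side and then asks whether the planned cells determine the patient-level comparison.

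**Step 1. What each output gives**

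| Output | Unit counted | Denominator | Split by severity or relationship? |
|---|---|---|---|
| T14.1.11 overall summary | Subjects in the upper rows; unclear from the *AEs reported* row down | Not stated | Yes, plus death and serious AE rows |
| T14.1.12 by body system | Events and patients | Safety population | No |
| T14.1.13 by relationship | Events | Arm's total events | Relationship |
| T14.1.14 by severity | Events | Arm's total events | Severity |
| T14.1.15 serious AEs | Events | None | Serious AEs only |
| L16.2.7 listing | Individual AEs by patient | None (listing) | Both, plus a serious AE flag |

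T14.1.11 is the only summary that might fill the gap. Its mild, moderate, severe, not related and related rows sit directly beneath *AEs reported*, which suggests events. Its footnote counts a subject once per system organ class and once per preferred term, but the table has no such rows. The footnote does not mention worst severity or closest relationship.

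**Step 2. Do the printed cells fix the number of patients?**

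Inputs: 125 patients per arm (SAP section 5, number randomized; the Safety population is assumed equal to it). All event counts are assumed, for illustration only.

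Formulas: printed percentage = related events / all events in the arm; patient incidence = patients with at least one related AE / 125. Patient counts are compared with the two-sided Fisher exact test.

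*Case A: identical cells, different incidence.* Each arm has 40 AEs, 10 of them related.

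- Printed in T14.1.13: 10/40 = 25.0%, so 10 (25.0%) under N = 40 in both arms.
- If these arose in 10 Test and 2 Reference patients: 10/125 = 8.0% versus 2/125 = 1.6%, p = 0.034.
- If they arose in 2 Test and 10 Reference patients: 1.6% versus 8.0%, p = 0.034, and the table is unchanged.
- Range: 10 related events can come from any number of patients between 1 and 10, so the one cell fits an incidence anywhere from 1/125 = 0.8% to 10/125 = 8.0%.

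Reading T14.1.12 alongside does not generally settle this. If the 10 related events in an arm all carry different preferred terms, T14.1.12 shows one patient per term whether they came from 10 patients or 2. The row for any AE can match as well, if patients with only unrelated AEs make up the difference.

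*Case B: opposite direction.* Test has 10 related of 50 AEs and Reference has 4 of 10, each related AE in a different patient.

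- Printed percentages: 10/50 = 20.0% versus 4/10 = 40.0%, which seems to favour Test.
- Patient incidence: 10/125 = 8.0% versus 4/125 = 3.2%, higher on Test (p = 0.17).

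The same arithmetic applies to severity in T14.1.14.

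**The case against.** The other side has several good points.

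- **Event burden is visible.** A reader might infer that the tables hide any difference in AE burden between the arms. They do not. Cells are n (%) under a header that gives the event total. For example, 8 severe of 40 against 2 of 10 would print as 8 (20.0) under N = 40 and 2 (20.0) under N = 10, and the fourfold difference can be seen. In Case B, too, the counts 10 and 4 are printed. What is hidden is the clustering of events within patients, as in Case A.
- **T14.1.11 exists.** A reader might infer that no planned table addresses severe, related or serious AEs by patient. That is too strong. T14.1.11 opens with subject counts, its severity, relationship and serious AE rows show percentages, and a patient-level reading is possible. The supportable statement is that the denominator is undefined and the layout points at least as readily to events.
- **Part of the comparison is already patient-based.** T14.1.12 gives patients over the Safety population with Fisher p-values, for any AE and by preferred term.
- **The data are not lost.** L16.2.7 allows patient counts to be derived by hand, and SAP section 9 allows headers, variable names and footnotes to be modified.
- **There is no internal contradiction.** SAP 8.3.1 and the shells agree on event counts for these two tables. Protocol 11.8 does not expressly ask for patients cross-classified by severity or relationship, and it makes Fisher testing conditional on sufficient data.

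All of this stands and limits the point. It does not remove it: a listing is not a planned summary, an undefined denominator does not supply an incidence, and event counts do not give patient counts.

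**Conclusion.** The point holds as a reporting gap of modest size. As planned, the report will show how many related, severe and serious events occurred in each arm, and how many patients had any AE. It will not clearly show how many patients had a related, severe or serious one.

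The documents do not support a stronger conclusion that the safety comparison fails or that differences in event burden are concealed. The illustrations use assumed counts and a Safety population of 125 per arm. They show that the planned cells do not determine the patient-level comparison. They do not predict what the trial will find, and if few patients have repeated events the practical difference will be small. The primary equivalence analysis and the sample size are not affected.

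**What to change.** 1. In T14.1.13 to T14.1.15, add a column of patients n (%) with N = Safety population in the arm. Give it overall and by system organ class and preferred term.
2. Count each patient once per row: at worst severity in T14.1.14, and as related in T14.1.13 if any of that patient's events in the row is related.
3. Keep event counts as a separate column, as T14.1.12 already does, and label any event-based percentage as a share of events.
4. In T14.1.11, state the unit and denominator of the severity, relationship, death and serious AE rows.
5. Align the two event-count sentences in SAP 8.3.1 with the revised shells.

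Fisher tests on any related AE and any severe AE are optional. With few events they will have little power, and the proportions matter more than the p-values.

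The cost is a small change to shells and programs. Severity, relationship and the serious AE flag are already recorded by patient, so no new data are needed.
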